5.3 LIFESTYLE CONSIDERATIONS

Not applicable.

5.4 SCREEN FAILURES

If the patient fails to qualify for the study after signing the informed consent form, they will be considered a screen failure. Screen failures should be recorded on the electronic screening log along with the reason for disqualification. Patients who screen fail and are not randomized will be eligible to rescreen later. Patients should only be enrolled into the study once, therefore patients who have been randomized will not be eligible for future screening.

5.5 STRATEGIES FOR RECRUITMENT AND RETENTION

5.5.A Planned Recruitment Activities

The research strategy for the present study calls for the enrollment of up to N=20 adults (aged 18-70 years) with treatment-resistant depression over the two-year project period. Our total enrollment target of up to N=20 reflects individuals who are screened, eligible, and treated in the protocol. Anticipating screen fails, dropouts after enrollment and lost to follow-ups post-treatment, we plan to screen a total of N=40 individuals over the proposed 24-month recruitment period. This enrollment period provides for a highly feasible **~2 subjects screened and ~1 subject who complete baseline visits per month**, allowing for 2-month follow-up after the enrollment of last subject.

DAC has implemented a robust workflow for identifying and screening candidates for clinical research and employs direct-to-patient advertising through radio, newspaper, internet-based and other media outlets. A centralized programmatic intake process (under protocol **STUDY-10-00606; A Screening Protocol for Adult Patients with Mood and Anxiety Disorders, Chronic Medical Conditions, and Healthy Volunteers.**) is employed that includes a central phone line, a program-specific email, and a website featuring a web-based survey that patients can take to see if they qualify for studies. Individuals who contact DAC by completing the pre-screener online survey are automatically entered into a secure web-based database in order to be contacted by a member of the research staff for additional screening.

In addition to recruiting individuals through the DAC centralized programmatic intake process, recruitment is also anticipated from the following additional sources: (1) patients with MDD who are currently receiving clinical care from providers (psychiatrists and psychologists) in DAC; (2) the Mount Sinai Hospital Adult Outpatient Psychiatry Clinic; (3) self-referrals from patients who have completed other research protocols through DAC; (4) clinicians within and outside of the Mount Sinai Health System, including large departments of psychiatry at Mount Sinai Beth Israel, Mount Sinai West, Mount Sinai Morningside, and Mount Sinai South Nassau; and (5) self-referrals from individuals attending community outreach programs in the New York State and tristate area and from media advertisements. The PI will review subject enrollment at weekly project meetings with the study coordinator and team members, so that any deviation from the anticipated enrollment schedule will be detected quickly. All outreach and advertising activities will also be reviewed on a weekly basis.

5.5.B Engagement Strategies for Retention

The PI will hold weekly project meeting with the study coordinator in order to monitor enrollment and ensure that enrolled subjects are completing all study procedures as intended.

In terms of infrastructure, the data coordinating facilities at ISMMS provides a secure, validated, centralized electronic data management facility that is HIPAA and FDA-compliant (Research Electronic Data Capture, or REDCap). The REDCap system employed in this study includes several components, including a Screening Database and a Subject Tracking Database, in addition to the Study Database proper. As subjects complete visits, the date of the visit will be entered into the database. Missed visits will be coded for reason (such as ill, scheduling problem, inability to contact, etc.). If subjects terminate early, the date and reason will be coded in the Subject Tracking Database. On a weekly basis, the study research coordinator, who will also function as the data manager, will run a report on patient accrual

and completion status for review by the PI and the team. On an ongoing basis, the study data manager, the PI, and other team members will review the status of patient accrual and retention, as well as form completion, to identify and resolve any bottlenecks or problem areas that arise during the course of the study.

At DAC, the study coordinator will be the subject's point of contact during the study. Subjects will be provided with phone and email contact information for their coordinator, in addition to the contact information for the study PI.

5.5.C Strategies that will be used to ensure a diverse, representative study sample

The ISMMS is part of a large urban medical center, and benefits from a large and diverse catchment area. Located in the Manhattan borough of New York City, the racial and ethnic distribution of Mount Sinai's catchment area is 49% Hispanic, 38% African American, and 13% white non-Hispanics. The catchment area of the Mount Sinai's affiliated hospitals in Queens and the Bronx includes 22% Hispanics, 23% white non-Hispanics, 26% Asians and 24% African Americans. For the proposed clinical trial there are no special restrictions with regard to ethnicity or race. It is expected that the study sample will closely approximate the racial and ethnic composition of the greater catchment area of the Mount Sinai Health System.

5.5.D Potential recruitment/enrollment challenges and strategies that can be implemented in the event of enrollment shortfalls

Anticipated study related barriers may involve issues including staff workload and scheduling windows. This will be addressed by including coordinators who serve as back-up for the primary study coordinator responsible for the proposed project. These back-up staff members will allow the study team to screen and enroll subjects and complete study visits within subject's availability. All study staff will be trained by the PI and study procedures will be reviewed at weekly project meetings to ensure consistency of study procedures across both primary and back-up study personnel.

Some participant related barriers include appointment scheduling, transportation issues, and maintaining contact between study visits. To ensure that subjects can attend appointments, whenever possible, the visit schedule will include flexibility. To help address transportation issues, the study team will offer patients metro cards and other transportation resources available through DAC. The research staff will check voicemail and email daily to be able to respond to any patient contact and will reach out before each scheduled appointment to ensure that subjects are still available and able to complete the visit as scheduled.

6 STUDY INTERVENTION

6.1 STUDY INTERVENTION(S) ADMINISTRATION

6.1.1 STUDY INTERVENTION DESCRIPTION

Izekizumab is a humanized immunoglobulin G subclass 4 (IgG4) monoclonal antibody (mAb) with neutralizing activity against IL-17A. Izekizumab is produced by recombinant DNA technology in a recombinant mammalian cell line and purified using standard technology for bioprocessing. Izekizumab is comprised of two identical light chain polypeptides of 219 amino acids each and two identical heavy

chain polypeptides of 445 amino acids each, and has a molecular weight of 146,158 Daltons for the protein backbone of the molecule.

Ixekizumab injection is a sterile, preservative free, clear and colorless to slightly yellow solution, for subcutaneous use available as 80 mg of ixekizumab in a 1 mL single-dose prefilled auto injector or a single-dose prefilled syringe. The prefilled auto injector and prefilled syringe each contain a 1 mL glass syringe with a fixed 27 gauge $\frac{1}{2}$ inch needle. The ixekizumab 80 mg prefilled auto injector and prefilled syringe are manufactured to deliver 80 mg of ixekizumab. Each mL is composed of ixekizumab (80 mg); Citric Acid Anhydrous, USP (0.51 mg); Polysorbate 80, USP (0.3 mg); Sodium Chloride, USP (11.69 mg); Sodium Citrate Dihydrate, USP (5.11 mg); and Water for Injection, USP. Ixekizumab solution has a pH of 5.3 – 6.1.

Ixekizumab is a humanized IgG4 monoclonal antibody that selectively binds with the interleukin 17A (IL-17A) cytokine and inhibits its interaction with the IL-17 receptor. IL-17A is a naturally occurring cytokine that is involved in normal inflammatory and immune responses. Ixekizumab inhibits the release of proinflammatory cytokines and chemokines.

6.1.2 DOSING AND ADMINISTRATION

Ixekizumab will be administered by subcutaneous injection. The dose is 160g (two 80 mg injections) at Week 0, followed by 80 mg at Weeks 2, and 4.

6.2 PREPARATION/HANDLING/STORAGE/ACCOUNTABILITY

6.2.1 ACQUISITION AND ACCOUNTABILITY

Ixekizumab will be obtained from commercial supplies by the Investigational Drug Service (IDS) at ISMMS.

6.2.2 FORMULATION, APPEARANCE, PACKAGING, AND LABELING

Ixekizumab injection for subcutaneous use manufactured by Eli Lilly.

Ixekizumab injection is a sterile, preservative free, clear and colorless to slightly yellow solution, for subcutaneous use available as 80 mg of ixekizumab in a 1 mL single-dose prefilled auto injector or a single-dose prefilled syringe. The prefilled auto injector and prefilled syringe each contain a 1 mL glass syringe with a fixed 27 gauge $\frac{1}{2}$ inch needle. The ixekizumab 80 mg prefilled syringe are manufactured to deliver 80 mg of ixekizumab. Each mL is composed of ixekizumab (80 mg); Citric Acid Anhydrous, USP (0.51 mg); Polysorbate 80, USP (0.3 mg); Sodium Chloride, USP (11.69 mg); Sodium Citrate Dihydrate, USP (5.11 mg); and Water for Injection, USP. The ixekizumab solution has a pH of 5.3 – 6.1.

6.2.3 PRODUCT STORAGE AND STABILITY

Ixekizumab injection is a sterile, preservative free, clear and colorless to slightly yellow solution available in a single-dose prefilled syringe to deliver 80 mg ixekizumab.

Ixekizumab is sterile and preservative-free. Discard any unused portion. Ixekizumab must be protected from light until use. Store refrigerated at 2°C to 8°C (36°F to 46°F). Do not freeze. Do not use Ixekizumab if it has been frozen. Do not shake. Discard the Ixekizumab single-dose syringe after use in a puncture-resistant container. Not made with natural rubber latex.

6.2.4 PREPARATION

Ixekizumab will be provided in a single dose prefilled syringe.

6.3 MEASURES TO MINIMIZE BIAS: RANDOMIZATION AND BLINDING

6.3.1 RANDOMIZATION AND BLINDING

This study will be open-label with one treatment condition. Given that this study is open label with one treatment condition, participants cannot be blinded.

6.4 STUDY INTERVENTION COMPLIANCE

An accurate and current accounting of the dispensing of study drug for each subject will be maintained on an ongoing basis by a member of the study site staff. The investigational site must keep an accurate inventory of study drug shipments received and the amount of study drug dispensed per patient on the Investigational Drug Accountability Record. At the end of the study, a full reconciliation of drug inventory will be performed. After a full reconciliation, any unused study drug will be destroyed by study personnel (if the site has the capability to do so, in accordance with applicable regulations) or sent to a designee for subsequent destruction. If no study drug remains, this will be indicated in the drug accountability log.

6.5 CONCOMITANT THERAPY

Participants will be permitted to remain on a stable dose of their psychotropic medications, per eligibility criteria. Concomitant treatments with other biologics or other immune-suppressant agents will be exclusionary. PRN use of NSAIDs is permissible.

6.5.1 RESCUE MEDICINE

Not applicable.

7 STUDY INTERVENTION DISCONTINUATION AND PARTICIPANT DISCONTINUATION/WITHDRAWAL

7.1 DISCONTINUATION OF STUDY INTERVENTION

A subject may be discontinued from study treatment at any time if the subject, the investigator, or the Sponsor feels that it is not in the subject's best interest to continue. The following is a list of possible reasons for study treatment discontinuation:

- Subject withdrawal of consent
- Subject is not compliant with study procedures

- Adverse event that in the opinion of the investigator would be in the best interest of the subject to discontinue study treatment
- Protocol violation requiring discontinuation of study treatment
- Lost to follow-up
- Sponsor request for early termination of study
- Positive pregnancy test (females)

Subjects who discontinue study treatment should come in for an early discontinuation visit as soon as possible. For patients who are lost to follow up, it may not be possible to complete early discontinuation procedures. For subjects who wish to withdraw consent, they will be asked to do so in writing following the completing of an early discontinuation visit. Some subjects may not agree and wish to withdraw consent immediately in which case these early discontinuation procedures may not occur. Reasonable attempts will be made by the investigator to provide a reason for subject discontinuation from study treatment.

7.2 PARTICIPANT DISCONTINUATION/WITHDRAWAL FROM THE STUDY

A subject may be withdrawn from the study at any time if the subject or the investigator-sponsor feels that it is not in the subject's best interest to continue. All subjects are free to withdraw from participation at any time, for any reason, specified or unspecified, and without prejudice.

Reasonable attempts will be made by the investigator to provide a reason for subject withdrawals. The reason for the subject's withdrawal from the study will be specified in the subject's source documents. As noted above, subjects who discontinue study treatment early (i.e., they withdraw prior to Visit 6) should have an early discontinuation visit.

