Secondary Endpoints: 1) Baseline-to-week-6 changes in depression severity as assessed by MADRS score; 2) Response and remission rates at week 6 (defined by $\geq 50\%$ MADRS total score improvement and MADRS total score of ≤ 10 , respectively); 3) Measures of global illness [Clinical Global Impression Severity (CGI-S) and Improvement (CGI-I) scale], overall depression [the Quick Inventory of Depressive Symptomatology Self-Report (QIDS-SR)], anxiety [Hamilton Anxiety Rating Scale (HAM-A)], suicidal ideation and attempt [the Columbia Suicide Severity Rating Scale (C-SSRS)], anhedonia [the Snaith Hamilton Pleasure Scale (SHAPS) and the Temporal Experience of Pleasure Scale (TEPS)], and symptoms associated with depression such as fatigue, sleep/wakefulness disturbances, anxiety, and irritability; 4) Baseline-to-week-6 changes in blood-based immune markers, like CRP and other immune markers

Exploratory Endpoints: Baseline-to-week-6 changes in RSFC will be evaluated with resting-state functional magnetic resonance imaging (MRI) scans. Baseline-to-week-6 changes in BBB permeability will be evaluated with dynamic contrast enhanced MRI.

Safety endpoints: 1) treatment-related adverse events; 2) Columbia-Suicide Severity Rating Scale at each time point

Study Population: Up to n=20 adults (Aged 18-70 years; male and female) with a primary diagnosis of MDD who have failed two adequate trials of medication in the current depressive episode. Demographics reflective of the greater NYC population.

Phase: Phase 2 study

[figure not shown]
Description of Sites/Facilities Enrolling Participants: The human research will be conducted at the Icahn School of Medicine at Mount Sinai (ISMMS). Research will be conducted at the Depression and Anxiety Center for Discovery and Treatment, the Clinical Research Unit (CRU), the Infusion Suite of the Psychiatry Department of ISMMS. Functional MRI scans will be completed at the BioMedical Engineering and Imaging Institute (BMEII) in the Hess Center for Science and Medicine.

Description of Study Intervention: One treatment condition in an open-label study design: ixekizumab 160 mg (two 80 mg subcutaneous injections) at Week 0, followed by 80 mg at Weeks 2 and 4.

Study Duration: The proposed study is to be completed in 24 months.

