2.3.1. C Psychological Screening Risks

Answering questions related to mental health and past experiences may be stressful. Research interviews will be interrupted if subjects become distressed or object to answering questions. If in the judgment of the PI or study-affiliated psychiatrist, the patient has worsened to such a degree that further participation would put the patient at risk, then the subject will be discontinued from the study and provided appropriate clinical care. Also, at any point during the study any subject meeting DSM-5 criteria for a manic episode or psychosis based on clinical interview by the Study PI or study-affiliated psychiatrist will be discontinued and provided appropriate clinical care.

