3 OBJECTIVES AND ENDPOINTS

OBJECTIVES	ENDPOINTS	JUSTIFICATION FOR ENDPOINTS
Primary		
The primary objective of the current study is to test the safety and feasibility of using ixekizumab in patients with TRD.	Completion of treatment measured as the receipt of all three Ixekizumab injections (160 mg at week 0, 80 mg at weeks 2 and 4). Drop-out rates will be calculated. The incidence and frequency of all anticipated and unanticipated serious and non-serious adverse events that occur between baseline and study exit visit will be determined. The effect of Ixekizumab will be assessed by changes in depression	Drop-out rates and treatment-related adverse events indicate the safety and tolerability of the study medication. The MADRS assessment is used as a gold-standard for assessing changes in depression

	severity as assessed with the Montgomery Asberg Depression Rating Scale (MADRS) scores from baseline to the end of treatment (EOT) visit (6-week post-treatment).	severity in clinical trials. The MADRS will be the primary endpoint of the study as we will use it to test the antidepressant effects of ixekizumab, our primary objective in the study.
Secondary		

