4. Record changes to concomitant medications.
5. Collect urine for a pregnancy test, (female subjects who are of childbearing age)
6. Perform self and clinician administered ratings scale:
 - MADRS
 - CSSRS-Since Last Visit
 - HAM-A
 - CGI-S
 - CGI-I
 - SHAPS
 - TEPS
 - QIDS-SR
7. Dispense study medication.

VISIT 3 (WEEK 4)

1. Obtain interval medical history.
2. Record any AEs.
3. Record changes to concomitant medications.
4. Record vital signs
5. Collect urine for a pregnancy test, (female subjects who are of childbearing age)
6. Perform self and clinician administered ratings scale:
 - MADRS
 - CSSRS-Since Last Visit
 - HAM-A
 - CGI-S
 - CGI-I
 - SHAPS
 - TEPS
 - QIDS-SR
7. Dispense study medication.

VISIT 4 (WEEK 6)

1. Obtain interval medical history.
2. Record any AEs.
3. Record changes to concomitant medications.
4. Perform self and clinician administered ratings scale:
 - MADRS
 - CSSRS-Since Last Visit
 - HAM-A

- CGI-S
- CGI-I
- SHAPS
- TEPS
- QIDS-SR

5. Perform a complete physical examination.
6. Perform and record vital signs.
7. Urine for urinalysis, urine toxicology, and pregnancy test (female subjects who are of childbearing age).
8. Collect blood for clinical laboratory tests and immunological measures.
9. Neuroimaging Procedures.

STUDY EXIT - VISIT 5 (WEEK 8)

10. Obtain interval medical history.
11. Record any AEs.
12. Record changes to concomitant medications.
13. Perform self and clinician administered ratings scale:
 - MADRS
 - CSSRS-Since Last Visit
 - HAM-A
 - CGI-S
 - CGI-I
 - SHAPS
 - TEPS
 - QIDS-SR

Note: This visit, including clinician administered rating scales, may be completed remotely via a HIPAA-compliant virtual platform.

Note: Study Visits 2, 3, and 4 are due to take place 2, 4, and 6 weeks after the baseline visit 1 (week 0) respectively. To allow for scheduling feasibility, Visits 1-5 can take place within 5 days before or after the scheduled visit.

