8.3.7 REPORTING EVENTS TO PARTICIPANTS

Participants will be notified of any abnormal clinical lab findings and directed to appropriate medical care. In the event that a participant's pregnancy test returns positive, the participant will be notified immediately and exited from the study.

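### Participants who stop ixekizumab early are not clearly kept on the week-6 and week-8 MADRS, C-SSRS and AE assessments, and two rules exit them outright

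*Combined protocol and SAP*

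**What the plan says.** Sections 7.1 (stopping study drug) and 7.2 (leaving the study) have separate headings, but 7.2 joins the two: "subjects who discontinue study treatment early (i.e., they withdraw prior to Visit 6) should have an early discontinuation visit". The schedule in 1.3 runs from V0 to V5, with the last dose at V3 (week 4) and study exit at V5 (week 8), so there is no Visit 6. After a stop, 7.1 prescribes one contact: "Subjects who discontinue study treatment should come in for an early discontinuation visit as soon as possible". That visit has no column in 1.3 and no entry in 8.2.

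The routes out differ in wording:
- **Worsening (2.3.1.C).** If the investigator judges that "further participation would put the patient at risk, then the subject will be discontinued from the study and provided appropriate clinical care". This is explicit exit, subject to that risk threshold.
- **Positive pregnancy test.** 8.3.7 says "the participant will be notified immediately and exited from the study", while 7.1 lists the same event as a reason to stop treatment.
- **Mania or psychosis (2.3.1.C).** The text ends "psychosis based on clinical interview by the Study PI or study-affiliated psychiatrist will be discontinued and provided appropriate clinical care", without saying from what.
- **Adverse events (7.1).** They are listed only as a reason to stop treatment.

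Safety is part of the primary objective. Section 3 counts "serious and non-serious adverse events that occur between baseline and study exit visit will be determined", and the safety endpoints in 1.1 include "Columbia-Suicide Severity Rating Scale at each time point". Section 9.3 assigns the secondary endpoints to all enrolled subjects, and 9.4.3 summarises MADRS on those observed.

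**The concern.** Those who stop for harm or deterioration are few, but their later ratings are among the most informative in a safety pilot. On the explicit exit rules, and on one available reading of 7.2, their week-6 and week-8 MADRS and C-SSRS ratings and any new AEs are not collected. The summaries then describe mainly those who did well enough to stay. The worsening rule also applies after dose 3: a participant who crosses its threshold between weeks 4 and 6 counts as a treatment completer but is exited before the week-6 outcome. Section 4.2 says the results are to inform a larger randomized trial. Ratings not taken at the time cannot be recovered at analysis.

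**Working it through.** **The plan's own figure.** Section 9.2 gives a 95% interval width of 0.35 for completion at n = 20 and p = 0.8. The Wald formula gives 2 × 1.96 × √(0.8 × 0.2 / 20) = 0.351, so it reproduces. This point does not touch it: someone who misses a dose is a non-completer, and someone who received all three is a completer, whether or not follow-up continues.

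**Is continued follow-up stated anywhere?** 1.3 and 8.2 list visits without distinguishing participants on drug from those off drug. Section 4.4 recognises those who complete all phases and those who exit by withdrawal, drop-out or screen failure; it names no off-drug, on-study status. 7.1 and 7.2 add only the early discontinuation visit. No sentence keeps a consenting stopper on weeks 6 and 8.

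**Ratings missed.** MADRS and the since-last-visit C-SSRS are scheduled at V1 to V5, five times. A stop with exit at week 2 misses weeks 4, 6 and 8 (3 of 5); at week 4 it misses weeks 6 and 8 (2 of 5). If the early discontinuation visit includes these scales, it may supply one unscheduled set.

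**Week-6 proportions.** If x responders are observed and k of 20 are missing, the all-enrolled proportion lies between x/20 and (x + k)/20. The width is k/20: 5, 10 or 15 percentage points for k = 1, 2 or 3. Three is the most that the expected early drop-out of under 20% in 9.2 allows, and it counts every leaver, including consent withdrawals and losses that no wording change can reach.

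**AE clocks, in nominal days.** 8.3.4 records non-serious AEs to 7 days and SAEs to 30 days after the last day of participation. 8.3.5 has SAEs reported to 30 days after the last dose. 9.4.1 counts time at risk to study exit or the end of the period of interest.

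| | Exit day 14 (dosed day 0) | Exit day 28 (dosed days 0, 14) | Kept to day 56 |
|---|---|---|---|
| Non-serious AE recording (8.3.4) | 14 + 7 = 21 | 28 + 7 = 35 | 56 + 7 = 63 |
| SAE recording (8.3.4) | 14 + 30 = 44 | 28 + 30 = 58 | 56 + 30 = 86 |
| SAE reporting (8.3.5) | 0 + 30 = 30 | 14 + 30 = 44 | unchanged |
| Patient-time (9.4.1) | 14 (25% of 56) | 28 (50% of 56) | 56 |

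Staying on study adds 42 days (63 − 21) or 28 days (63 − 35) of non-serious AE recording. SAE recording under 8.3.4 gains the same 42 or 28 days (86 − 44, 86 − 58). The 8.3.5 period gains none.

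**MADRS.** If k leavers would have improved D points less than stayers, the observed mean change overstates the all-enrolled mean by (k/20) × D. The documents give neither D nor a rate for these stops. For illustration only, one leaver with D assumed between 8 and 16 gives 0.4 to 0.8 points.

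**The case against.** The best defence is that the plan is less severe than the parenthesis in 7.2 suggests, and much of this stands.
- The worsening rule removes a patient only when continuing would put that patient at risk. Some of these patients could not be kept under any wording.
- For suicidality with marked illness or worsening, the C-SSRS text in 8.1 calls for a safety review that decides case by case whether the participant continues.
- 7.1 treats withdrawal of consent as a further step, made in writing after the early discontinuation visit.
- Known AEs are followed to resolution or stabilization. SAE recording under 8.3.4 reaches past week 6 for exit at day 14 and past week 8 for exit at day 28.
- Event rates use patient-time, so shorter observation enters the denominator.
- A participant exited between weeks 4 and 6 should have a discontinuation visit close to week 6.
- Secondary analyses are descriptive and report the number observed, so attrition will be visible.

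A reader might infer that every adverse-event stop ends participation, that mania and psychosis are study exits, or that AE follow-up ceases. The documents support none of these: 7.1 makes adverse events a treatment stop only, the mania and psychosis sentence is open, and the AE safeguards above are written down. Pregnancy is an explicit exit, but it is neither harm nor worsening, so it is no evidence of outcome-related loss.

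The defence does not supply any commitment to scheduled week-6 and week-8 assessments after a stop. AE follow-up protects events already known; it schedules no visit to detect new ones and no MADRS or C-SSRS rating. Showing how many are missing does not show how they fared.

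**Conclusion.** The point holds as a cheap improvement that the sponsor should make. Exit is explicit for a positive pregnancy test and for worsening that makes continuing risky. For adverse events, mania and psychosis the text is ambiguous. No provision keeps consenting stoppers on the scheduled assessments. Each one missing at week 6 leaves all-enrolled proportions undetermined by 5 percentage points, and each loses 42 or 28 days of non-serious AE recording for exit at day 14 or 28. These figures assume 20 enrolled, nominal visit days, and participation ending on the day of the stop; a later discontinuation visit would shorten the loss.

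Two stronger conclusions do not follow. The primary completion proportion is not biased. Nor can a particular overstatement of MADRS improvement be claimed, because its size rests on a difference and a stopping rate that the documents do not give.

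**What to change.** - In 7.1 and 7.2, separate stopping study drug from leaving the study.
- Make a positive pregnancy test, mania, psychosis and investigator-judged worsening mandatory drug stops, and align 2.3.1.C and 8.3.7 with this.
- Keep participants who retain consent on the scheduled week-6 and week-8 AE, C-SSRS and MADRS assessments, unless the investigator judges the visits themselves harmful. Do no contrast MRI after a positive pregnancy test.
- Flag scores after a stop as off-treatment, record other care started, and show the week-6 summaries with and without them.
- Correct Visit 6, and list the assessments of the early discontinuation visit.

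The cost is amended wording and at most two extra visits for each consenting stopper, with no new instruments and no change in sample size. Week 8 is already flexible: "This visit, including clinician administered rating scales, may be completed remotely via a HIPAA-compliant virtual platform". After a week-2 stop, the week-4 ratings would still be missed. The downside is that off-treatment scores may partly reflect other care, which is why both summaries are needed. The change also gives up the present choice to exit for pregnancy and for risky worsening, although the investigator can still end participation to protect a patient.
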